6. ASSESSMENT OF EFFICACY

6.1 Specification of efficacy variables.

The efficacy variables for improving neurological function would be the initial, intermediate and final comparison of:

- Partial and total values of the SARA scale (Scale for the assessment and grading of cerebellar function in ataxias).
- SCAFI index (composite Z-score) result of the transformation of the results of:
 - .. Average time to travel 8 meters round trip.
 - .. Time spent completing the 9-hole test with dominant and non-dominant hands.
 - .. Number of syllables PA-TA repeated in two series of 10 seconds.
- Total partial scores of the Barthel Index.
- Total score and each dimension of the SF36 quality scale.
- Increase in frataxin levels compared to baseline measurement figures.
- Significant change in the values of the mitochondrial proteins studied.

6.2 Methods and schedule for evaluation, registration and analysis of efficacy parameters.

- Evaluations of efficacy parameters will be carried out at the beginning, after 6 months and after one year of treatment for neurological function. The quality of life questionnaire and the Barthel index will be administered at the screening visit and after one year of treatment.
- The registration of these data will be carried out in the corresponding CRD.

- The parameters will be assessed and compared at the end of the study.

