3. TRIAL DESIGN

Given the purpose of the trial, the neurological function of the patients will be evaluated prior to the start of treatment, at 6 months and at 12 months. The duration is determined by the characteristics of the disease, which is neurodegenerative and therefore changes in neurological function are not expected until after a long period of time. Neurological function will be assessed using standardized tests aimed at assessing cerebellar motor function, gait, dysarthria and manual dexterity. This includes the SARA scale for assessing and grading cerebellar function, the eight-meter walk test (time taken by the patient to travel 8 meters in both directions and calculating round trip and average), a dexterity test, the 9-Hole Peg test (the time spent placing nine pegs in 9 holes, with the dominant and non-dominant hand, is assessed, and the PATA speed test, for assessing dysarthria, in which the number of times is counted that the patient emits these syllables in two periods of 10 seconds, calculating the number in each series and the average of both).

All these tests will be videotaped and the files obtained will be archived on an external hard drive for conservation, evaluation, reproduction and subsequent comparison. In this first visit, measures of activities of daily living will be taken using the Barthel Index and also the SF36 questionnaire (Spanish version of SF-36v2™).

Control visits will be made at 15 days, 4, 8 and 12 months, to check calcium levels (among other analytical determinations), symptoms of adverse effects, and ECG. Communication with patients will be facilitated with various methods (telephone, email) to assist them in any eventuality.

In these same visits and with the same extraction, samples will be obtained to determine frataxin levels. Frataxin will be quantified by western blot of platelet lysate.

In the same lysate, various mitochondrial proteins will be quantified by SRM-based mass spectrometry.

3.1 Specific description of the main and secondary variables.

As primary variables, the parameters obtained from the aforementioned neurological function tests will be specifically evaluated: SARA scale values, time to travel 8 meters, time to complete the 9-hole test, number of syllables of the dysarthria test.

Secondary variables will be evaluated: calcium levels and kidney function, frataxin levels, Barthel index values and SF36 quality of life questionnaire.

3.2 Description of the type of trial.

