The present study is a pilot study aimed at verifying the effects of treatment with calcitriol on neurological function, calcium levels, frataxin levels, and quality of life in patients with FA.

This is an open study, all patients will receive treatment, and the results obtained before and after treatment will be compared, using parameterized tests and video filming.

3.3 Description of trial treatment.

The drug used, calcitriol, is on the market under the registered trademark Rocaltrol®. The lowest dose will be used: 25 micrograms, orally once a day for one year (Rocaltrol 0.25 micrograms soft capsules, presented in a PVC blister containing 20 capsules).

3.4 Expected duration of participation and all trial periods.

The study will continue over one year.

It will begin with a recruitment period, a screening period that includes the evaluation of inclusion and exclusion criteria, the assessment of neurological function, a determination of calcium, vitamin D, kidney function, albumin, proteins, sodium, potassium, phosphate, and pregnancy test in pre-menopausal women, and extraction for basal determination of frataxin, evaluation of the quality of life questionnaire. An ECG will also be performed.

The treatment period will begin from here.

Fifteen days after the start of this, the next visit will be carried out with the first extraction for determination of frataxin, calcium, kidney function, sodium, potassium, phosphate, ECG and assessment of possible symptoms related to possible adverse effects of the treatment.

This procedure will be repeated at 4, 8 and 12 months with determination of frataxin, calcium, albumin, kidney function, ECG and assessment of possible symptoms related to possible adverse effects of the treatment (Addendum 6).

After 6 months of treatment, the first assessment of neurological function will be carried out.

At the last visit of the 12 months, a new assessment of neurological function, Barthel index and final quality of life questionnaire will also be carried out (Addendum 5.1, Addendum 5.2, Addendum 5.3 and Addendum 5.4).

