Post-study follow-up, the data obtained will be analyzed and its statistical evaluation will be carried out. Patients who wish to continue treatment will be allowed to continue, at least until the first results of the comparison of the initial neurological function with the second and final ones are obtained. If the results obtained are positive, treatment will be maintained in these patients with regular analytical controls. If the result does not demonstrate a statistically significant result, this will be discontinued in all patients. Detection of hypercalcemia will lead to immediate withdrawal from the study.

If possible, patients who show improvement will be followed up in our Ataxia Unit.

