9.2 Statistics methods

A descriptive analysis will be carried out using the usual statistics: mean and standard deviation, or median and interquartile range for quantitative variables with non-normal distribution. The normality of the data will be checked using the Shapiro-Wilks test and/or Q-Q plots. The qualitative variables will be described according to the number and percentage of subjects in each category.

The effect of treatment with calcitriol on neurological function will be evaluated using a mixed linear model with the levels of neurological function tests as a dependent variable and the measurement time (screening, 6-month control and final control) as an independent variable included as an effect. random. To take into account possible confounding effects, covariates will be introduced as fixed effects. The same analysis will be repeated for frataxin levels and other biochemical parameters in platelets.

Comparison of baseline frataxin levels between healthy controls and patients with ataxia will be carried out using the Student's t test for independent data or the Mann-Whitney U test, if the data do not meet the assumption of normality. The relationship between the increase in frataxin production and clinical improvement will be

evaluated using a logistic regression model where the dependent variable will be defined dichotomously by jointly evaluating frataxin levels against increases of more than one point on the scale. SARA, two or more points of the SCAFI composite index (which would add the results of the 8 m walk test, time taken from the 9-HPT, the number of syllables from the PATA test), the values of the Barthel Index in 10% and the SF36 questionnaire by 20% on the values obtained in the first evaluation.

The results will be expressed in odds ratio (OR).

The effect of treatment with calcitriol on the quality of life of the patients at the beginning and end of treatment will be evaluated through the t-student test for paired data or the Wilcoxon test, if normality is not met in the distribution of the data.

To assess toxicities, a table of frequencies of occurrences will be created.

Statistical analysis will be performed with o IBM SPSS Statistics version 26 and R software.

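### SARA part-scores and SF36 dimensions rank level with their totals as efficacy variables, with no error control or exploratory label, so testing them as listed materially inflates the false-positive rate

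*Combined protocol and SAP*

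**What the plan says.** Section 6.1 gives one flat list of efficacy variables. Three entries concern multi-part scales:

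- SARA: "Partial and total values of the SARA scale"
- Barthel: "Total partial scores of the Barthel Index"
- SF36: "Total score and each dimension of the SF36 quality scale"

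The SARA and SF36 entries expressly put the total and its parts side by side. The Barthel entry is garbled. It may mean total and partial scores, but that is an inference.

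Section 3.1 does rank the scales. The primary tier reads "As primary variables, the parameters obtained from the aforementioned neurological function tests will be specifically evaluated: SARA scale values", followed by the other neurological tests. The secondary tier reads "Secondary variables will be evaluated: calcium levels and kidney function, frataxin levels, Barthel index values and SF36 quality of life questionnaire". Section 2.2(c) also places Barthel and SF36 among the secondary objectives. Neither section separates a total from its parts.

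Section 9.2 assigns a mixed linear model to the neurological tests. For SF36 it says "The effect of treatment with calcitriol on the quality of life of the patients at the beginning and end of treatment will be evaluated", using a paired t-test or the Wilcoxon test. It states no alpha, sidedness, testing order or multiplicity adjustment, and calls no score exploratory. It does not say whether each part-score will be tested.

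Section 3.4 gives significance a consequence. After referring to the comparison of neurological function over the study, it says "If the result does not demonstrate a statistically significant result, this will be discontinued in all patients". It does not name the score.

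**The concern.** When a total and all its parts have equal standing and the number of tests is left open, the team can decide after seeing the data which scores to test and report. One SF36 dimension or one SARA part-score that crosses 5% by chance could then be presented as an effect of calcitriol even if the total did not move.

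Two things depend on this. Secondary objective (c) asks about quality of life, and section 1 says that positive results would lead to larger trials. More directly, the rule in section 3.4 on continuing treatment turns on a significant neurological result. Because section 3.1 names SARA values without saying total, a SARA part-score could supply that result.

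This point concerns the ranking within each scale. The choice among the four primary neurological tests, and the mitochondrial protein panel, are separate matters.

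**Working it through.** **The plan's own figure.** The plan states no error rate. Its one related number is the sample size in section 9.1, which reproduces: 24–40 × 0.5 = 12–20, and 12/0.80 to 20/0.80 = 15–25. With 20 patients planned and 20% loss, 20 × 0.80 = 16 remain. The check therefore uses 16 to 20 patients.

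**Inputs.** From the documents: the SF36 entry in section 6.1, the paired test in section 9.2, and one before-after comparison (SF36 is given at screening and at one year, section 6.2). Assumed, because the documents do not give them:

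- eight SF36 dimensions plus a total, so k = 9 tests
- two-sided 5% for each test
- no true mean change
- normally distributed change scores with equal correlation between them

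**Independent scores.** The chance of at least one false positive is 1 − (1 − α)^k.

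- Either direction: 1 − 0.95^9 = 0.370.
- Gains only (2.5% in that tail): 1 − 0.975^9 = 0.204.

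**Correlated scores.** Dimensions of one questionnaire are correlated, which lowers the rate. Simulation of 40,000 trials per cell, with a paired t-test on each score, gives for k = 9:

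| Correlation | Either direction, n = 20 | Either direction, n = 16 | Gains only, n = 20 |
|---|---|---|---|
| 0 | 0.373 | 0.374 | 0.205 |
| 0.3 | 0.332 | 0.328 | 0.168 |
| 0.5 | 0.276 | 0.278 | 0.137 |
| 0.8 | 0.176 | 0.174 | 0.088 |

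Against the nominal level, the ratio at correlation 0.5 is 0.276/0.05 = 5.5 for either direction and 0.137/0.025 = 5.5 for gains only. At correlation 0.8 both ratios are about 3.5.

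**Sensitivity.** A separate simulation with the eight dimensions alone (20,000 replicates, n = 20) gives 0.261 for either direction and 0.132 for gains only at correlation 0.5. At correlation 0.9 these fall to 0.121 and 0.059. The count of 8 or 9 matters little; the correlation matters more.

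**What is not calculated.** No figure is given for SARA, because section 9.2 plans a three-time-point mixed model for it and the documents do not count its parts. None is given for Barthel, because its entry in section 6.1 is unclear and section 9.2 has no stand-alone Barthel test.

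**The case against.** The strongest reply is that section 6.1 lists variables and defines no success rule, and that section 9.2 never says each sub-score will be tested. Where section 9.2 does set improvement thresholds, for the logistic regression, it names SARA, SCAFI, Barthel and SF36 as wholes and no dimension or item. The trial is also an open, uncontrolled pilot ("The present study is a pilot study aimed at verifying the effects of treatment with calcitriol on neurological function"), so a before-after change could not be attributed to calcitriol by its p-value alone, adjusted or not.

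Much of this stands, and it rules out four stronger readings.

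- A reader might infer that a chance improvement is likely. The gains-only rate is about 14%, and at most about 21% under the assumptions used.
- A reader might infer that the protocol has no hierarchy at all. Sections 2.2(c) and 3.1 set primary and secondary tiers; only the ranking within a scale is missing.
- A reader might infer that one significant sub-score formally counts as efficacy. No passage says so; the plan leaves it open.
- A reader might add up tests over all three scales for a larger rate. The documents support neither the counts nor a Barthel test.

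The reply does not close the gap. An undefined number of tests is part of the problem, because it leaves the choice open until the data are seen. The pilot label applies to the whole trial and marks no score as exploratory. Section 3.4 still uses significance to decide something. That rule concerns neurological function, so it bears mainly on SARA and much less on SF36.

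**Conclusion.** The point holds in a limited form. SARA part-scores and SF36 dimensions stand level with their totals, and no section ranks, adjusts or labels them. If the SF36 scores are tested as listed, the chance of at least one false significant result is about 28% at correlation 0.5 (17% at 0.8 to 37% at zero), and about 14% for gains only (9% to 21%). This is material inflation over 5% and 2.5%, but it does not make a false improvement probable.

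The figures rest on the assumed nine tests, the 5% level and zero true change. Progression in a neurodegenerative disease would lower the chance of an apparent gain, and open-label expectation could raise it. The practical weight falls most on SARA because of section 3.4. The plan should be changed on this point, though the pilot status moderates its seriousness.

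**What to change.** In sections 3.1, 6.1 and 9.2:

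- Name the total of each scale as the only score tested for inference: the SARA total, the SF36 total and, once its entry is clarified, the Barthel total. The existing primary and secondary tiers can stay.
- State alpha and sidedness.
- Label SARA part-scores, SF36 dimensions and any Barthel part-scores exploratory, and report them as mean change with 95% confidence intervals.
- State that no effect is claimed from a part-score when its total is not significant.

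Part-scores then add no formal type I error, so no further adjustment of them is needed. The cost is a few sentences and no new data or patients. The small downside is that an isolated sub-score change can be reported only as hypothesis-generating.

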7. SAFETY ASSESSMENT

7.1 Specifying security variables.

- The main safety variable is the determination of corrected calcium levels, measured simultaneously with albumin and proteins at all visits.
- Another variable is the anomalies of the ECG that will be carried out and checked at each visit.
- The deterioration of neurological function at the 6-month visit, or at the time it occurs and can be attributed to the treatment, with no other cause found to justify it (fever, intercurrent illness, etc.).

7.2 Methods and schedule for evaluation, recording and analysis of security parameters.

En el control visitado en 15 days, 4, 8 y 12 months, the following must be evaluated:

- . Calcium, albumin, kidney function, sodium, potassium and phosphate levels.
- . ECG.

The data obtained will be registered in the corresponding CRD.

The normality or not of the corrected calcemia parameters will be assessed.

Hypercalcemia, depending on its severity, can cause increased contractility, arrhythmias, and atrioventricular block. For this reason, the typical ECG abnormalities in hypercalcemia will be especially evaluated: shortening of the QT, especially shortened QTc (defined as the period from the beginning of the QRS to the end of the T wave) and other alterations: increased duration of the wave T (severe hypercalcemia), increased amplitude of the QRS complex, elevation of the ST segment, arrhythmias.

All these parameters will be assessed in each ECG compared with the baseline recording.

7.3 Reporting of adverse events and intercurrent illnesses and registration of adverse reactions.

Adverse events and intercurrent illnesses will be recorded in the corresponding section of the CRD.

Serious adverse events will be especially noted on a separate sheet (Adendum 7).

Each serious adverse event will be reported to the corresponding authorities.

7.4 Type and duration of follow-up after adverse events (AEs).

- Patients with adverse effects will be followed until resolution. If the AE is mild and does not require attention by the researchers, follow-up will be carried out remotely. Otherwise, the patient will be examined at our center in an out-of-program visit.
- If it is a serious adverse effect, the patient will be followed until it is resolved, the necessary means will be put in place to solve it. Subsequently, the serious adverse effect form will be filled out and said SAE will be communicated through the Spanish Pharmacovigilance System for medicines for Human Use: www.notifyam.es.

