4.4. Subject withdrawal criteria.

Will be removed from the study:

- to. Any patient who presents hypercalcemia during the controls carried out throughout the trial.
- b. Subjects who present with ECG abnormalities indicative of possible hypercalcemia or arrhythmias during treatment with calcitriol.
- c. Those who repeatedly skip taking treatment.
- d. Those affected who present a new disease or require supplementary treatment that may make the interpretation of the results difficult.

Patients with hypercalcemia and those with ECG abnormalities will continue to be monitored until resolution of symptoms or recorded abnormalities (see Addendum 6).

Telephone or email contact will also be maintained with the patients in section d), although they will not re-enter the study.

Controls with those in section c) will not be followed.

A notification of a serious adverse effect will be made if this occurs (see Addendum 7).

The date of withdrawal from the study and the reason for this, as well as the evolution followed by the patient, will be noted in the CRD.

Subjects who drop out of the study will not be replaced by others as long as the "n" of the study remains between 15 and 20.

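### Section 7.4 places the serious adverse event form and its external report after follow-up to resolution, and no other section says when the report is due

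*Combined protocol and SAP*

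**What the plan says.** Three sections of the combined protocol and SAP deal with serious events.

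- **Section 4.4 (withdrawal criteria):** "A notification of a serious adverse effect will be made if this occurs (see Addendum 7"). The event itself prompts the notification. No deadline is given.
- **Section 7.3 (reporting of adverse events):** "Serious adverse events will be especially noted on a separate sheet (Adendum 7"), and "Each serious adverse event will be reported to the corresponding authorities". The duty covers every serious event and has no condition on outcome. No deadline is given here either.
- **Section 7.4 (type and duration of follow-up):** "If it is a serious adverse effect, the patient will be followed until it is resolved", with a clause on taking whatever measures are needed to deal with it. The next sentence is "Subsequently, the serious adverse effect form will be filled out and said SAE will be communicated through the Spanish Pharmacovigilance System".

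Section 10 (ethical considerations) mentions calcium measurement, ECG and ease of contact as safeguards, and does not mention when serious events are reported. Addendum 7, cited in 4.4 and 7.3, is not in the text available for review.

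**The concern.** The purpose of prompt reporting is that people outside the site can judge a serious event while other patients are still being treated. If the report waits for resolution, that judgement comes after the event is over. The longer and graver the event, the longer the wait.

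This matters more than usual here. Section 1.4 presents the trial as the first in vivo study of this effect in these patients, with tolerability and safety among the things to be learned. Section 1.2 names cardiac dysfunction as the leading cause of death in the disease. Section 7.2 lists arrhythmias and atrioventricular block as possible consequences of hypercalcaemia, and section 5.4 foresees hospital admission for its more severe forms. Up to 20 patients are to be treated for 12 months. The schedule puts recruitment before treatment, so they would be on the drug largely in parallel. The available text describes no independent safety committee, so external reporting is the only outside check that it sets out.

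**Working it through.** No arithmetic applies. The check is to read the order of steps and then look for any other rule on timing.

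**Step 1: the order in 7.4.** Read in sequence, the section gives:

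1. follow to resolution and manage the event;
2. complete the form;
3. communicate the event to the pharmacovigilance system.

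The word that opens the second sentence puts steps 2 and 3 after step 1.

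**Step 2: other sources of timing.**

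| Section | Is reporting required? | What prompts it | Time limit | Initial report, then follow-up |
|---|---|---|---|---|
| 4.4 | Yes | The event occurring | None | Not mentioned |
| 7.3 | Yes, for each event | Not stated | None | Not mentioned |
| 7.4 | Yes | Comes after follow-up to resolution | None | Not mentioned |
| 10 | Not addressed | – | – | – |

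Sections 4.4 and 7.3 establish that a report is made. Only 7.4 places it in a sequence, and none of them counts time from onset or from awareness.

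**Step 3: the delay that follows.** Under the order in 7.4, the time from awareness to external report is the remaining duration of the event plus the time to complete the form. Neither term is bounded in the documents.

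**Step 4: events with no clear resolution date.** For a death, resolution is not defined. For a permanent after-effect, the first step has no natural end. There is also a tension for patients withdrawn for repeatedly missing treatment: 4.4 says their controls are not continued, while 7.4 expects follow-up to resolution. If 4.4 governs, resolution might not be observed in such a patient.

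**Step 5: what the delay does not reach.** Section 7.3 records adverse events in the case record as a separate step. Section 8.2 says that the database holds all the fields of that record. Section 9.2 tabulates toxicities by frequency. None of these waits for the external report. Section 3.5 gives the promoter as the joint Neurology Service, which also prescribes the drug.

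**The case against.** The strongest case on the other side has four parts.

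**The sections must be read together.** Section 4.4 ties notification to the event occurring, and 7.3 requires it for each event. A site reading all three must report a death. This stands. A reader might infer that a fatal or permanent event would go unreported altogether, or that 7.4 cancels the duty in 7.3. The documents do not support either inference. What remains is that neither 4.4 nor 7.3 says when, so they do not remove the delay.

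**The wording is a rough translation.** The clause just before the second sentence of 7.4 is about dealing with the event, so the intended meaning may be to treat first and then report. That is a possible reading. However, the same sentence opens with follow-up to resolution ("the patient will be followed until it is resolved, the necessary means will be put in place to solve it"), and a site has only the text in front of it. A sequence open to both readings still needs correcting.

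**Addendum 7 may carry a deadline.** It could, and so could the general undertaking in section 11.2 to take account of current Spanish requirements. The addendum has not been seen, and the undertaking sits in the funding section and sets no time. If the addendum does give a clock, 7.4 would still have to be brought into line with it.

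**Two consequences might be overstated.** A reader might infer that the gravest events would be missing from the safety table, or that the sponsor could not act. Neither follows. The case record is kept separately, and the promoter is the service that treats the patients. Only outside bodies would learn late.

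**Conclusion.** The point holds as a defect in the order and timing of external reporting. As written, 7.4 lets the report to the pharmacovigilance system wait for the length of the event, with no upper limit, and leaves the timing undefined for fatal or unresolved events. Sections 4.4 and 7.3 keep the duty to report intact but set no clock.

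The size can be stated only in that form. It is tempting to convert the delay into further exposure of the other patients. That would need an event duration and a count of patients still on treatment. The documents give neither, and 4.4 withdraws patients while 9.1 allows for a 20% loss.

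The conclusion rests on two assumptions: that the second sentence of 7.4 means what it says in sequence, and that Addendum 7 does not already set an earlier deadline. If the second fails, the point reduces to a contradiction between the addendum and the body text. The change should be made because it concerns patient safety and costs almost nothing. It does not affect the validity of the efficacy analysis.

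**What to change.** Reword 7.4 in two sentences:

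- The investigator completes and sends an initial serious adverse event report on becoming aware of the event, whatever its outcome, within a stated time limit counted from awareness. The documents give no limit, so the sponsor must supply the one that applies.
- The patient is then followed to resolution, and a later report gives the outcome, with fatal and not resolved among the permitted categories.

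Refer to this timing from 4.4 and 7.3, and check that Addendum 7 has room for an initial and a follow-up report and gives the same deadline. State in 4.4 that the end of controls for patients withdrawn for missed treatment does not end follow-up of an open serious event, or otherwise reconcile it with 7.4.

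The cost is two sentences in 7.4, the cross-references, and one short follow-up report per event. Sample size, visits and analysis are unchanged.
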